Treatment efficacy for anxiety and depression will be assessed by the State-Trait Anxiety Inventory (**STAI**), Hospital Anxiety and Depression (**HAD**) scale, Brief Profile of Mood States (**POMS-SR**), Beck Depression Inventory (**BDI**), and Brief Symptom Inventory (**BSI**). The STAI, HAD, POMS-SR, BDI, and BSI will also be re-administered at the following time points: T1, T4-T12. In addition, regarding a broad assessment of affective states, the Positive and Negative Affect Schedule Expanded Form (**PANAS-X**), a 60-item questionnaire, will be administered to assess for positive and negative affect. This scale will be re-administered at the following time points: T6 (2-weeks after drug administration) and T12 (26-weeks after drug administration). The STAI, HAD and BDI will be re-administered at T13 and T14.

Pain

Treatment efficacy for pain perception will be assessed by the Brief Pain Inventory – Short Form (**BPI-SF**), and the Memorial Symptom Assessment Scale (**MSAS**) (only questions relevant to anxiety, depression or pain symptoms) will be administered two weeks prior to the experimental treatment session, the day before, 7-hours after each drug administration session, the day after, two weeks after the session, and then every month for the next six months. In addition, the Memorial Sloan Kettering Pain Card (**MSKCC**) will be self-administered by the subjects every day from two weeks before the treatment session until six weeks after, including just before psilocybin administration and at four and seven hours afterward. Subjects' use of pain medications will be closely monitored throughout the study duration.

Attitudes towards disease progression and death

Attitudes towards disease progression and death will be measured at baseline with the following measures: Death Transcendence Scale (**DTS**), Demoralization Scale (**DEM**), Death Anxiety Scale (**DAS**), and the Hopelessness Assessment and Illness (**HAI**) scale. These measures will also be obtained at the following time points: T6 (2-weeks after drug administration) and T12 (26-weeks after drug administration). The DEM, DAS and HAI will be re-administered at T13 and T14.

Quality of Life/Spirituality:

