concern, expression of positive emotions, and self-confidence (Griffiths et al. 2006). The COM-R will also be assessed at the following time points: T7, and T12. Due to observers' availability, it is expected that the administration of the COM-R may not occur on the exact scheduled time point. However, every effort will be made to conduct this assessment as close to the required time points as possible.

Measures assessed 1 day before the sessions (T₁):

The STAI, HAD, POMS-SR, BDI, and BSI will be administered to assess for anxiety and depressive symptoms. As mentioned above, regarding pain assessment, the BPI-SF, MSAS, and MSKCC will be administered one day prior to the sessions as well.

Measures assessed just before drug administration (T₂):

The only measure to be administered will be the MSKCC to assess for pain.

Measures assessed throughout the sessions:

Ten minutes before and 30,60,90,120,180,240,300, and 360 minutes after capsule administration, monitor ratings, blood pressure, and heart rate will be obtained.

Blood pressure and heart rate:

Blood pressure (systolic, diastolic, and mean arterial pressure) and heart rate will be monitored.

Monitor rating questionnaire:

At the same points in time in which the above physiological measures will be obtained, the two session monitors will complete the Monitor Rating Questionnaire, which involves rating 20 dimensions of the subject's mood or behavior on a five-point Likert scale from 0 to 4.

Measure assessed 4 hours after drug administration (T₃):

The only measure to be administered will be the MSKCC to assess for pain.

Measures assessed 7 hours after drug administration (T₄):

The STAI, HAD, POMS-SR, BDI, and BSI will be administered to assess for anxiety and depression, and the BPI-SF, MSAS, and MSKCC will be administered to assess for pain.

Changes in state of consciousness will be assessed with the altered states of consciousness rating scale **5D-ASC** (Dittrich 1998; Dittrich, Lamparter et al. 1999), which is a scale suited to depict alterations in waking consciousness — including changes in mood, perception, experience of self and environment, and thought disorders — regardless of the inducing factor(s) (Dittrich 1996; Dittrich 1998). In addition, the Hallucinogen Rating Scale (**HRS**) will be administered, a 100-item scale used to assess altered states of consciousness produced by serotonergic hallucinogens such as psilocybin (Strassman 1994; Riba 2001).

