Regarding the assessment of enduring changes in attitudes and affect, the Persisting Effects Questionnaire (**PEQ**), an 89-item questionnaire, will be administered to assess changes in attitudes, moods, behavior, and spiritual experience (Pahnke 1969; Richards 1977). The categories of inquiry from this questionnaire include: positive attitudes about life and/or self, negative attitudes about life and/or self, positive mood changes, negative mood changes, altruistic/positive social effects, and antisocial/negative social effects. In addition, regarding a broad assessment of affective states, the Positive and Negative Affect Schedule Expanded Form (**PANAS-X**), a 60-item questionnaire, will be re-administered.

Measures relating to quality of life, spirituality and forgiveness will be re-assessed with the FACIT, PIL, WHO-Bref, WHO-SPRB, and the Forgiveness Questionnaire.

The Kast questionnaire will be re-administered to assess for the quality of the drug administration experience.

The DTS, DEM, DAS, and HAI will be re-administered to assess for attitudes towards disease progression and death.

Measures assessed 6 weeks after drug administration (T₇):

The STAI, HAD, POMS-SR, BDI, and BSI will be administered to assess for anxiety and depression, and the BPI-SF, MSAS, and MSKCC will be administered to assess for pain.

Regarding community observer ratings of changes in subjects' behavior and attitudes, the above-mentioned structured interview (COM-R) will be re-administered.

Measures assessed 10 weeks after drug administration (T₈):

The STAI, HAD, POMS-SR, BDI, and BSI will be administered to assess for anxiety and depression, and the BPI-SF, and MSAS, will be administered to assess for pain.

Measures assessed 14 weeks after drug administration (T₉):

The STAI, HAD, POMS-SR, BDI, and BSI will be administered to assess for anxiety and depression, and the BPI-SF, and MSAS, will be administered to assess for pain.

Measures assessed 18 weeks after drug administration (T₁₀):

The STAI, HAD, POMS-SR, BDI, and BSI will be administered to assess for anxiety and depression, and the BPI-SF, and MSAS, will be administered to assess for pain.

Measures assessed 22 weeks after drug administration (T₁₁):

The STAI, HAD, POMS-SR, BDI, and BSI will be administered to assess for anxiety and depression, and the BPI-SF, and MSAS, will be administered to assess for pain.

Measures assessed 26 weeks after drug administration (T₁₂):

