According to a recent study by Moreno and colleagues, published in 2006, in patients with refractory Obsessive Compulsive Disorder (OCD), an anxiety spectrum disorder, it was found that, with psilocybin, subject's mean YBOCS scores were reduced to 10.67 at 24 hours from 24.11 +/- 6.3 at baseline (Moreno 2006). This represents a reduction of 2 in effect size (assuming a 0.5 correlation between baseline and 24 hours). If we assume placebo has no effect on anxiety, depression and pain, a sample size of 16 subjects in each group (in the first treatment session) will provide 75% power to detect a reduction of 1 effect size, and > 99% power at 2 effect sizes, at the 5% level. This power analysis shows that even if patients dropout before the second cross-over session, the total of 31 patients in the first session will have adequate power for the study endpoints.

Regarding the effect of psilocybin on the outcome variables measuring anxiety, the STAI and HAD scale, analyses will be conducted using a paired t-test to evaluate the effect of treatment over time. The comparisons will be between the following time points: (T0 & T1)-T4, (T0 & T1)-T5, (T0 & T1)-T6, and (T0 & T1)-T7. The comparisons between the active agent and placebo groups will be conducted using an independent sample t-test to look at differences on the STAI and HAD scale measures. Similar analyses will be conducted both within and between groups for the other outcome measures, assessing for depression (POMS-SR, BSI and BDI scales) and pain (BPI-SF, MSAS, and MSKCC scales).

To assess the interaction between drug and time, a series of repeated measures multivariate analyses of variance (MANOVA) will be used to compare the active drug and placebo study arms across time in terms of the major outcome variables during the first and second randomized experimental treatment sessions. Both treatment main effects across time and interactions of treatment with time will be assessed in the repeated measures MANOVA.

Longer-term effects will be measured in two ways looking at the outcome measures of anxiety, depression, and pain. First the effect of time will be assessed with a MANOVA analysis from baseline relative to T7-T12. Also, MANOVA will be used to look at the effect of sequencing of getting the active agent vs. placebo in a sequence x time analysis from baseline relative to T7-T12.

Data Management and Statistics:

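### About 90% of the daily MSKCC pain-card readings, including T2 and T3, enter no named comparison, so available precision on a secondary outcome is forgone

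*Combined protocol and SAP*

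**What the plan says.** The Pain paragraph under the T0 measures says the MSKCC card "will be self-administered by the subjects every day from two weeks before the treatment session until six weeks after". On the session day three readings are scheduled, at T2, T3 and T4. For T2 (just before dosing), and again for T3 (4 hours), the protocol states: "The only measure to be administered will be the MSKCC to assess for pain".

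The Statistical Analyses section sets out the anxiety tests first: "The comparisons will be between the following time points: (T0 & T1)-T4, (T0 & T1)-T5, (T0 & T1)-T6, and (T0 & T1)-T7", with an independent-sample t-test between arms. It continues: "Similar analyses will be conducted both within and between groups for the other outcome measures", and lists BPI-SF, MSAS and MSKCC as the pain scales.

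Two further analyses could bear on the card. A repeated-measures MANOVA will "compare the active drug and placebo study arms across time in terms of the major outcome variables during the first and second randomized experimental treatment", that is, in both sessions; it lists no time points and does not name the card. For longer-term effects on anxiety, depression and pain, "First the effect of time will be assessed with a MANOVA analysis from baseline relative to T7-T12". At T8 to T12, however, "the BPI-SF, and MSAS, will be administered to assess for pain"; the card has stopped by then.

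The section also promises descriptive statistics and graphs for every outcome measure. No mean, area under the curve, slope or mixed model is described for the diary.

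**The concern.** Pain is part of the study hypothesis and a named secondary outcome. Patients with current or past cancer are asked for a card every day for about eight weeks around a session, yet the named tests use only the card values at six time points. If one day's card represents each visit, the comparison carries the full day-to-day noise, and one missed card loses that visit for that patient.

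T2 and T3 raise a second point. T2 is the closest pre-dose value, and T3 is the only scheduled pain rating in the first hours after dosing. Neither appears in a named contrast. With no diary summary fixed in advance, the averaging window could also be chosen after the data are seen.

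**Working it through.** **Plan's own figure.** The plan states 75% power at 1 effect size with 16 per group at the 5% level, and a first-session total of 31. A two-sample t-test (noncentral t, two-sided 5% assumed) gives 78.1% for 16+16, 76.7% for 16+15 and 75.3% for 15+15. The 75% is thus reproduced to within 2 points at the stated total of 31. It does not rest on averaged diary values.

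**Count of card readings per session window.**
- Days: 14 before + 1 session day + 42 after = 57.
- Readings: 14 + 42 + 3 on the session day (T2, T3, T4) = 59.
- Used in named contrasts: T0, T1, T4, T5, T6, T7 = 6. Unused: 53/59 = 89.8%.
- T0 falls 2-4 weeks before session 1, while the diary starts at two weeks. If T0 precedes the diary, 5 are used and 54/59 = 91.5% are not.
- If the session MANOVA takes in T2 and T3, 8 are used and 51/59 = 86.4% are not.

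**Same count over all pain records.** BPI-SF and MSAS are each given 11 times (T0, T1, T4-T12). Total 59 + 11 + 11 = 81, of which 6 + 22 = 28 are used; 53/81 = 65% are not. Up to T7 only: 59 + 6 + 6 = 71, 18 used, 53/71 = 75% not.

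**What averaging could gain.** The documents give no SD or day-to-day correlation for the card, so everything here is assumed: a constant effect of 0.7 single-day SD, 16 v 15 patients, two-sided 5%, a stable patient share ρ of the single-day variance, and lag-1 autocorrelation φ of the remainder.

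Variance of an m-day mean = ρ + (1-ρ)·g(φ,m), where g is the average of φ^|i-j| over all pairs of days i, j. Power is taken at 0.7/SD.

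Score test, single day: SD 1, power 47%. With a 7-day mean:

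| ρ | φ | g | SD | Power |
|---|---|---|---|---|
| 0.5 | 0 | 0.143 | 0.76 | 70% |
| 0.8 | 0.4 | 0.288 | 0.93 | 53% |
| 0.8 | 0.8 | 0.641 | 0.96 | 50% |
| 0.8 | 0.9 | 0.798 | 0.98 | 48.5% |
| 0.9 | 0.9 | 0.798 | 0.99 | 48% |

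Change score, with r the pre/post correlation of the stable level (0.6-0.8). The correlation of daily noise between the baseline and outcome windows is ignored.
- Planned: one post-dose day minus the mean of T0 and T1. Variance = 2ρ(1-r) + (1-ρ)(1 + g_b), where g_b is about 0.5 for two days far apart.
- Windows: 7-day outcome mean minus 14-day baseline mean. Variance = 2ρ(1-r) + (1-ρ)(g(φ,7) + g(φ,14)).

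| ρ | r | φ | Planned SD, power | Window SD, power |
|---|---|---|---|---|
| 0.5 | 0.8 | 0 | 0.98, 49% | 0.55, 92% |
| 0.8 | 0.8 | 0.4 | 0.79, 67% | 0.64, 84% |
| 0.5 | 0.6 | 0 | 1.07, 42% | 0.71, 75% |
| 0.8 | 0.6 | 0.8 | 0.97, 49% | 0.93, 53% |
| 0.5 | 0.6 | 0.8 | 1.08, 42% | 0.97, 49% |

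Power rose in every case run, by under 1 point to 23 points for the score and by 4 to 44 points for the change.

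**Session overlap.** Sessions are 7 to 8 weeks apart, so session 2's pre-session diary begins on day 35 to 42 and shares 8 to 1 days with session 1's diary. A window ending on day 42 still closes before session 2 (day 49 at the earliest).

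**The case against.** Four objections have weight.

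First, a reader might infer that 90% of the pain data goes unused. The documents do not support that. BPI-SF and MSAS are compared at T4 to T7 and enter the long-term pain MANOVA; across all pain records the share without a named analysis is about 65-75%. Nor is the rest of the diary strictly unused, since descriptive displays are promised for every outcome, and the session MANOVA does not exclude T2 and T3. What stands is that no inferential summary of the diary is named.

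Second, a reader might infer that planned power is lost. It is not: the stated 75% never relied on averaged cards. A possible gain is forgone, and its size is assumed throughout. With strong autocorrelation or a high stable share the score-test gain is only 1-3 points. Entry requires anxiety but no stated pain level, and patients in remission are eligible, so many cards may sit near zero and the model may fit poorly.

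Third, that one day's card stands for a visit is itself a reading. The plan does not say which card value represents T6 or T7.

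Fourth, averaging changes the question. If the effect fades with a 7-day half-life, the mean over days 8-14 is about 1.37 times the day-14 value, so it overstates status at exactly two weeks. A mean over all 42 days would keep only 25% of the day-1 effect and could lose power. That argues for short windows ending at the visit day.

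**Conclusion.** The point holds for the MSKCC card. About 53 of 59 readings per session window (86-92%, depending on how T0, T2 and T3 are treated) enter no named comparison, and neither MANOVA nor the descriptive displays supplies a diary summary. The count follows from the documents.

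The gain in precision rests on assumptions they do not supply: for an effect of 0.7 single-day SD and 16 v 15 patients, 47% to about 48-70% on the score (ρ 0.5-0.9, φ 0-0.9), and 42-67% to about 49-92% on change (ρ 0.5-0.8, φ 0-0.8, r 0.6-0.8). This is one of three pain scales, and pain is a secondary outcome in a pilot. The change is worth making because the data are already collected.

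**What to change.** In the Statistical Analyses section, for the MSKCC card only and for the first-session comparison, state:
- Baseline: the mean of available daily cards in the 14 days before session 1.
- Outcomes: the mean of available cards on days 8-14 (for T6) and on days 36-42 (for T7), with T5 kept as planned.
- Test: compare the arms on these means with the baseline mean as covariate, which should add some precision beyond the change-score figures above.
- Session day: compare the arms on T3 and T4 relative to T2, and say whether T2 and T3 also enter the session MANOVA.

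The cost is analysis wording only: no new visit, form or patient. The downside is small. The T6 and T7 card results become preceding-week averages and should be labelled so, and the gain will be slight if daily scores are highly autocorrelated or many patients report little pain.

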The primary objective of this double-blind, placebo-controlled pilot study is to assess the efficacy of psilocybin administration (4-phosphoryloxy-N,N-dimethyltryptamine), a serotonergic psychoactive agent, on psychosocial distress, with the specific primary outcome variable being anxiety associated with cancer. Secondary outcome measures will look at the effect of psilocybin on symptoms of pain perception, depression, existential/psychospiritual distress, attitudes toward disease progression, quality of life, and spiritual/mystical states of consciousness. In addition, a secondary objective of the study is to determine the feasibility of administering psilocybin to this patient population, with regards to the following issues: safety, patient recruitment, consent for treatment, and retention. The duration of the proposed investigation will be long enough to administer the drug one time to each of thirty-two patients and to conduct follow-up assessments. This study would be separate but similar to a completed study at the Los Angeles Biomedical Research Institute at Harbor-UCLA Medical Center, run by a psychiatrist, [name], and an oncologist, [name]. Although the outcomes measures would be similar to those used as in the Grob study, the proposed dose of psilocybin would be somewhat higher at 0.3mg/kg and the total number of subjects randomized for the study would be 31 instead of 12 (see below explanation and justification). This study has been approved by the Bellevue Psychiatry Research Committee, the Oncology PRMC Committee, the Food and Drug Administration (FDA) through the issuance of an IND (77,138), the NYU IRB and the NYU-HHC Clinical and Translational Science Institute (CTSI) (previously known as the Bellevue General Clinical Research Center GCRC).

Hypothesis/Potential Mechanism of Action:

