This is a pilot study of a single treatment designed to preliminarily evaluate the effect of psilocybin in patients with cancer and anxiety. Secondary outcome measures will be pain perception, depression, and existential / psychospiritual distress. Also, issues related to the feasibility of using psilocybin in patients with cancer and anxiety will be described. The study will look at both short-term, immediate effects as well longer-term effects. We plan to collect and analyze data up to 6-months post the second drug administration for all enrolled participants. Participants who complete a psilocybin dosing session and agree to be contacted will be invited to partake in two optional data collection time points, which will look at long-term psychological effects of psilocybin-assisted psychotherapy.. Subjects’ participation in these two additional longitudinal timepoints will be optional and will not affect their previous study involvement as research participants. Study participants who opt out or who do not have the option to participate (for example, if they are deceased) will be classified (ie study completers, withdrawn, treatment dropout, etc.) as they were in the main portion of the study. Participants do not need to complete all questionnaires given at previous time points to be eligible to participate in optional time points T13 and T14.

Criteria for patient selection (Inclusion/Exclusion Criteria)

The proposed project will involve up to 47 subjects 18-76 years of age. Subjects will have a current or historical diagnosis of cancer with a projected life expectancy of approximately 6 months or more and a DSM-IV psychiatric diagnosis, as determined by the Structural Clinical Interview for DSM-IV (SCID), of one of the following Anxiety Disorders: Acute Stress Disorder, Generalized Anxiety Disorder, Anxiety Disorder Due to cancer, or Adjustment Disorder with Anxiety. The cancer could be: at any stage of active illness; potentially life

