In the first six weeks following the experimental treatment sessions, several follow-up meetings (at least 3 for a total minimum of 6 hours) in person between the subject, the study staff and the monitors will be arranged to facilitate psychological integration of the psilocybin experience, as well as to administer the research measures. Additional meetings in person or on the telephone will be held at least monthly intervals for further follow-up for six months. The principal investigator will be the primary contact person for the subjects.

Communication with community observers (i.e. family members, friends, co-workers) will be part of follow-up as a way to get an objective measure of patient outcome in addition to self-report.

Drug Conditions

Psilocybin and niacin will be administered in identically appearing opaque, size 0 gelatin capsules with approximately 180ml of water. The dose of psilocybin will be 0.3mg/kg and the niacin dose will be 250mg. Each subject will participate in two experimental treatment sessions. In the study, approximately half of the subjects will be randomized to receive psilocybin (n=15 or 16) or the placebo, niacin (n=15 or 16). Following

the first treatment session of either the active agent or placebo, a cross-over design will be instituted with the alternative drug administered on the second session. Subjects and treatment personnel will be blinded for each experimental drug administration. The time interval between the two experimental treatment sessions will be 7 weeks (+ 1 week).

For both experimental treatment sessions, patients will be weighed as close as possible to the day before the session, and the dose of psilocybin will be mixed and compounded the day prior to the drug administration session at 0.3mg/kg (- 4 day window). Regarding niacin, it too will be mixed and compounded the day before the drug administration session (- 4 day window).

Justification for 0.3mg/kg dose of psilocybin

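### The stated 75% power at 16 per group is not what the planned t-test gives (78.1%), and the randomised number differs by one patient (31 or 32) between sections

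*Combined protocol and SAP*

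**What the plan says.** Under Statistical Analyses (Including Power Analysis), the plan assumes no placebo effect and states that "a sample size of 16 subjects in each group (in the first treatment session) will provide 75% power to detect" a reduction of one effect size, "and > 99% power at 2 effect sizes, at the 5% level". The paragraph closes by saying that, even with dropout before the second session, "the total of 31 patients in the first session will have adequate power for the study endpoints". The test behind the power figure and its sidedness are not given. The next paragraph names an independent-samples t-test for comparing active drug with placebo.

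The number of patients appears in three other places:

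- The opening section, in a sentence on study duration, allows time to "administer the drug one time to each of thirty-two patients".
- The same section, comparing the trial with the earlier study of 12 patients, says "the total number of subjects randomized for the study would be 31 instead of 12".
- Drug Conditions says about half will "receive psilocybin (n=15 or 16) or the placebo, niacin (n=15 or 16"), that is, 15 + 16 = 31.

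Separately, Criteria for patient selection says: "The proposed project will involve up to 47 subjects 18-76 years of age".

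**The concern.** Two things do not fit together.

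1. The power sentence ties 75% to 16 per group, yet the test the plan names gives a higher value at that size.
2. The calculation is made for 2 × 16 = 32 patients, while the conclusion in the next sentence is drawn for 31. The opening section shows the same difference of one: if 31 are randomised, 32 cannot be dosed.

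The randomised number and its power are the figures against which enrolment and dropout are later judged, and the safety board's planned review covers both. A reader checking the power paragraph finds a percentage that does not match its sample size, and a sample size that does not match the conclusion drawn from it.

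**Working it through.** **Inputs**

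- Significance level 0.05, from the power paragraph. Sidedness is not stated; two-sided is assumed and one-sided is also tried.
- Standardised effect d = 1 (and d = 2), from the power paragraph.
- Group sizes: 16/16 from the power paragraph; 16/15 from Drug Conditions and the total of 31; 15/15 for comparison.
- Test: independent-samples t-test, from the analysis paragraph.

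**Source of the effect size.** The cited obsessive-compulsive disorder study had a mean of 24.11 (SD 6.3) at baseline and 10.67 at 24 hours. With correlation 0.5 and equal SDs, the SD of change is 6.3 × √(2 − 2 × 0.5) = 6.3. The effect is (24.11 − 10.67)/6.3 = 2.13, so the plan's figure of 2 is reproduced.

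**Formula.** Noncentrality δ = d × √(n₁n₂/(n₁+n₂)), with n₁+n₂−2 degrees of freedom. Power is the probability that a noncentral t variable with that δ falls outside ± the 97.5% point of the central t.

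**The plan's own figures at 16/16**

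- d = 2: δ = 2 × √(256/32) = 5.657 and power is 99.98%. The claim of more than 99% is reproduced.
- d = 1: δ = √8 = 2.828, df = 30, critical value 2.042 and power is 78.1%. The stated 75% is not reproduced; the gap is 78.1 − 75 = 3.1 points.

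**Power at d = 1, 5% level, by group size**

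| Groups | Total | δ | t-test, two-sided | Normal approximation, two-sided | t-test, one-sided |
|---|---|---|---|---|---|
| 15/15 | 30 | 2.739 | 75.3% | 78.2% | 84.8% |
| 16/15 | 31 | 2.782 | 76.7% | 79.5% | 85.8% |
| 16/16 | 32 | 2.828 | 78.1% | 80.7% | 86.8% |

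None of these three methods gives 75% at 16/16; all give more. The planned two-sided t-test gives 75.3% at 15/15. For 31 patients it gives 76.7%, which is 1.7 points above the stated value.

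**Other methods.** A two-sided Mann-Whitney test at 16/16 with normal data gives 74.8% by simulation (20,000 runs), or 76.1% using its asymptotic relative efficiency of 0.955. The plan does not name that test.

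**Patient numbers side by side**

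| Place | Number | Total |
|---|---|---|
| Opening section, duration sentence | thirty-two dosed | 32 |
| Opening section, comparison with earlier study | 31 randomised | 31 |
| Drug Conditions | 15 or 16 per arm | 31 |
| Power paragraph, calculation | 16 per group | 32 |
| Power paragraph, conclusion | 31 in first session | 31 |

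There are two candidate totals, one patient apart, and three of the five places support 31.

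**Fewer evaluable patients (illustration only).** The plan expects some non-completion but gives no rate. If 14/14 were evaluable in the first session, power at d = 1 would be 72.1%; at 13/13 it would be 68.7%. These sizes are assumptions and do not come from the plan.

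**The case against.** The strongest reply is that nothing turns on this. The design delivers at least the power it states: 78.1% for 32 patients and 76.7% for 31, against 75% claimed. The companion figure at two effect sizes is reproduced at every group size from 15/15 to 16/16. In a pilot study, a gap of 1.7 to 3.1 points changes no decision. That stands in full, and it limits the point to a correction of wording.

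A second reply is that 75% need not be an arithmetic error, because the method is unstated. A Mann-Whitney calculation gives about 75% at 16/16. Under the normal approximation, 75% would fit 14/14 (75.4%) and not 15/15. This also stands in part. It is tempting to infer that 75% was computed for 15 per group and attached to the wrong number. The documents do not support that inference; they show only that the planned t-test does not give 75% at 16/16. A Mann-Whitney basis would also not be the analysis the plan describes.

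A third reply is that a reader can tell which number is meant, since most places point to 31. That is fair. What remains is a difference of one patient between the outlying places and the rest.

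A reader might also count the ceiling of 47 as a further conflicting sample size. The documents do not support that. It is an upper limit on subjects involved, whereas 31 is expressly the number randomised. Subjects can leave in between: the plan excludes those scoring below 8 on the baseline Hospital Anxiety and Depression scale and drops those without sufficient rapport before the first session. Going from 47 to 31 would mean losing 16/47 = 34%, and to 32, 15/47 = 32%. The plan gives no rate to compare with these, so the link is unexplained but not contradictory.

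**Conclusion.** The point holds as a minor inconsistency. The 75% paired with 16 per group is not reproduced by the plan's own between-group test, which gives 78.1%, assuming a two-sided 5% level and d = 1. The randomised number is inconsistent by one patient: 31 and thirty-two within the opening section, and 32 in the power calculation against 31 in its conclusion.

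The power error is conservative. It should not be read as showing that the trial is underpowered or that the adequacy statement fails: with 31 patients split 16 and 15, power is 76.7%, above the stated figure. This finding concerns only the internal agreement of the figures; it takes no view on whether an effect of 1 is a realistic target.

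**What to change.** - Use one randomised number in the opening section, in Drug Conditions and in both sentences of the power paragraph.
- In the power paragraph, name the test and say whether it is one- or two-sided.
- Restate the matching power. For a two-sided 5% independent-samples t-test at an effect size of 1, this is 77% for 31 patients (16 and 15), or 78% if 32 (16 and 16) is intended. The figure of more than 99% at two effect sizes can stay.
- Optionally, say what the ceiling of 47 counts (for example consented or screened subjects) and how it leads to the randomised number.
- If power for fewer evaluable first-session patients is added, label it illustrative unless an expected dropout rate is also given.

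The cost is wording only: no extra patients and no change to the design or analysis.
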